12.2 Responsibilities of the investigator and IRB/IEC

Before initiating a trial, the investigator/institution must obtain approval/favorable opinion from the Institutional Review Board/Independent Ethics Committee (IRB/IEC) for the trial protocol, written informed consent form, consent form updates, patient recruitment procedures (e.g. advertisements) and any other written information to be provided to patients. Prior to study start, the investigator is required to sign a protocol signature page confirming his/her agreement to conduct the study in accordance with these documents and all of the instructions and procedures found in this protocol and to give access to all relevant data and records to Novartis monitors, auditors, Novartis Quality Assurance representatives, designated agents of Novartis, IRBs/IECs, and regulatory authorities as required. If an inspection of the clinical site is requested by a regulatory authority, the investigator must inform Novartis immediately that this request has been made.

For multi-center trials, a Coordinating Investigator will be selected by Novartis around the time of Last Patient Last Visit to be a reviewer and signatory for the clinical study report.

12.3 Publication of study protocol and results

The key design elements of this protocol will be posted in a publicly accessible database such as clinicaltrials.gov. In addition, upon study completion and finalization of the study report, the results of this trial will be either submitted for publication and/or posted in a publicly accessible database of clinical trial results.

13 Protocol adherence

This protocol defines the study objectives, the study procedures and the data to be collected on study participants. Additional assessments required to ensure safety of patients should be administered as deemed necessary on a case by case basis. Under no circumstances is an investigator allowed to collect additional data or conduct any additional procedures for any research related purpose involving any investigational drugs under the protocol.

Investigators ascertain they will apply due diligence to avoid protocol deviations. If an investigator feels a protocol deviation would improve the conduct of the study, this must be considered a protocol amendment, and unless such an amendment is agreed upon by Novartis and approved by the IRB/IEC and health authorities, where required, it cannot be implemented.

All significant protocol deviations will be recorded and reported in the CSR.

Isolated ALT or AST elevation > 5 to ≤ 8 × ULN	
Isolated ALT or AST elevation > 3 to ≤ 5 × ULN (patient is asymptomatic)	
 Monitor liver chemistry tests two or three times weekly
Isolated ALP elevation	
 Repeat liver chemistry tests within 48-72 hours If elevation is confirmed, measure fractionated ALP; if >50% is of liver origin, establish hepatic causality Complete CRFs per liver event guidance
Any AE potentially indicative of liver toxicity	
 Consider study treatment interruption or discontinuation Hospitalize if clinically appropriate Complete CRFs per liver event guidance

Table 15-3 Exclusion of underlying liver disease

Disease	Assessment
Hepatitis A, B, C, E	
 IgM anti-HAV; HBSAg, IgM anti-HBc, HBV DNA; anti-HCV, HCV RNA, IgM & IgG anti-HEV, HEV RNA
CMV, HSV, EBV infection	
 IgM & IgG anti-CMV, IgM & IgG anti-HSV; IgM & IgG anti-EBV
Autoimmune hepatitis	
 ANA & ASMA titers, total IgM, IgG, IgE, IgA
Alcoholic hepatitis	
 Ethanol history, γGT, MCV, CD-transferrin
Nonalcoholic steatohepatitis	
 Ultrasound or MRI
Hypoxic/ischemic hepatopathy	
 Medical history: acute or chronic CHF, hypotension, hypoxia, hepatic venous occlusion. Ultrasound or MRI.
Biliary tract disease	
 Ultrasound or MRI, ERCP as appropriate.
Wilson disease	
 Caeruloplasmin
Hemochromatosis	
 Ferritin, transferrin
Alpha-1-antitrypsin deficiency	
 Alpha-1-antitrypsin

16 Appendix 2: Specific Renal Alert Criteria and Actions

Table 16-1 Specific Renal Alert Criteria and Actions

Criteria	Action required
Serum creatinine (sCr) increase 25 – 49% compared to baseline	
 Consider causes and possible interventions Follow up within 2-5 days
Serum creatinine increase > 50%	
 Consider causes and possible interventions Repeat assessment within 24-48h if possible Consider drug interruption or discontinuation unless other causes are diagnosed and corrected Consider hospitalization and specialized treatment
Protein-creatinine or albumin-creatinine ratio increase \geq 2-fold or new onset dipstick proteinuria \geq 1+ or Albumin-creatinine ratio (ACR) \geq 30 mg/g or \geq 3 mg/mmol; or Protein-creatinine ratio (PCR) \geq 150 mg/g or >15 mg/mmol	
 Consider causes and possible interventions Assess serum albumin & serum protein Repeat assessment to confirm Consider drug interruption or discontinuation unless other causes are diagnosed and corrected
New onset glucosuria on urine dipstick (unless related to concomitant treatment, diabetes)	
Assess & document:
 
 Blood glucose (fasting) Serum creatinine Urine albumin-creatinine ratio
New hematuria on dipstick	
Assess & document:
 
 Urine sediment microscopy Assess sCr and urine albumin-creatinine ratio Exclude infection, trauma, bleeding from the distal urinary tract/bladder, menstruation Consider bleeding disorder

Additional specialized assessments are available to assess renal function or renal pathology. (Note: In exceptional cases when a nephrologist considers a renal biopsy, it is strongly recommended to make specimen slides available for evaluation by Novartis to potentially identify project-wide patterns of nephrotoxicity.)

Whenever a renal event is identified, a detailed patient history and examination are indicated to identify, document and potentially eliminate risk factors that may have initiated or contributed to the event:

- Blood pressure assessment (after 5 min rest, with an appropriate cuff size)
- Signs and symptoms such as fever, headache, shortness of breath, back or abdominal pain, dysuria, hematuria, dependent or periorbital edema
- Changes in blood pressure, body weight, fluid intake, voiding pattern, or urine output
- Concomitant events or procedures such as trauma, surgical procedures, cardiac or hepatic failure, contrast media or other known nephrotoxin administration, or other potential causes of renal dysfunction, e.g., dehydration, hemorrhage, tumor lysis

Table 16-2 Follow-up of renal events

Action	Follow up
Assess*, document and record in the Case Report Form (CRF) or via electronic data load. Review and record possible contributing factors to the renal event (co-medications, other co-morbid conditions) and additional diagnostic procedures (MRI etc) in the CRF.	
 • Urine dipstick and sediment microscopy • Blood pressure and body weight • Serum creatinine, electrolytes (sodium, potassium, phosphate, calcium), bicarbonate and uric acid • Urine output
Monitor subject regularly (frequency at investigator's discretion) until:	
 • Event resolution: (sCr within 10% of baseline or protein-creatinine ratio within 50% of baseline) 
or
 
 • Event stabilization: sCr level with $\pm 10\%$ variability over last 6 months or protein-creatinine ratio stabilization at a new level with $\pm 50\%$ variability over last 6 months.

* Urine osmolality: in the absence of diuretics or chronic kidney disease this can be a very sensitive metric for integrated kidney function that requires excellent tubular function. A high urinary osmolality in the setting of an increase in sCr will point toward a "pre-renal" cause rather than tubular toxicity.

## 1 Introduction

### 1.1 Scope of document

The RAP documents contain detailed information to aid the production of Statistics & Programming input into the Clinical Study Report (CSR) for trial “**CBYM338X2211**”.

The Statistical Analysis Plan (SAP) describes the implementation of the statistical analyses planned in the protocol.

### 1.2 Study reference documentation

Final study protocol (v05) is available at the time of finalization of SAP.

### 1.3 Study objectives

#### 1.3.1. Primary objective(s)

Primary objective(s)	Endpoints related to primary objectives

 
To evaluate the treatment effect of bimagrumab on total body fat mass
 
	
 
Body fat mass by DXA at Week 48
 

#### 1.3.2. Secondary objective(s)

Secondary objective(s)	Endpoints related to secondary objective(s)

 
To evaluate the treatment effect of bimagrumab on total body fat mass after 6 months of treatment
 
	
 
Body fat mass by DXA at Week 24
 

 
To evaluate the treatment effect of bimagrumab on glycemic control and parameters of insulin sensitivity
 
	
 
HbA1c, fasting glucose and insulin, HOMA2-IR, QUICKI, Matsuda index based on MTT at Week 24 and Week 48
 

 
To evaluate the safety and tolerability of bimagrumab in overweight/obese patients with type 2 diabetes.
 
	
 
Adverse events, Vital Signs, ECG, Laboratory Values, Immunogenicity
 

 
To evaluate the pharmacokinetics of repeat doses of bimagrumab in overweight/obese patients with type 2 diabetes.
 
	
 
PK samples – pre (Ctrough) and post dose during treatment and follow-up periods. Tmax and Cmax (Day 1, Day 168 and Day 308) will be derived.
 

 
To evaluate the immunogenic response to repeat dosing of bimagrumab in overweight and obese patients with type 2 diabetes.
 
	
 
Anti-bimagrumab antibodies pre-dose, during treatment and at the end of study.
 

---

• To evaluate the treatment effect of bimagrumab on anthropometric body measurements and on lean body mass

	

• Body weight, BMI, waist circumference, waist-to-hip ratio, lean body mass (LBM) by DXA at Week 24 and at Week 48

--	--

---

***1.3.3. Exploratory objective(s)***

Company Confidential Information

Company Confidential Information

[figure not shown]
### 1.4 Study design and treatment

This is a non-confirmatory, randomized, subject and investigator blinded, placebo-controlled, parallel arms study, investigating a 48-week treatment period with intravenous bimagrumab 10mg/kg in overweight/obese patients with type 2 diabetes. Approximately 68 patients (34 receiving active treatment and 34 placebo) are planned to be enrolled and randomized. The randomization will be stratified according to baseline BMI in two strata:

- BMI between 28 kg/m^2 and 33 kg/m^2 (inclusive) and
- BMI above 33 kg/m^2 and up to 40 kg/m^2 (inclusive),

in order to achieve an approximate balance of BMI distribution across the two treatment groups.

Figure 1-1: Study Design

Based on the latest version of protocol amendment, an additional visit at week 2 has been added coded as Visit 115.

## 2 First interpretable results (FIR)

Company Confidential Information

Company Confidential Information

### **3 Interim analyses**

Company Confidential Information

### **4 Statistical methods: Analysis sets**

For all analysis sets, patients will be analyzed according to the study treatment(s) received.  
The safety analysis set will include all patients that received any study drug.

The PK analysis set will include all patients with at least one available valid (i.e. not flagged for exclusion) PK concentration measurement, who received any study drug and experienced no protocol deviations that impact PK data.

The PD analysis set will include all patients with available PD data, who received any study drug and experienced no protocol deviations with relevant impact on PD data.

For subjects for which the actual treatment received does not match the randomized treatment, the treatment actually received will be used for the analysis. The analysis sets and protocol deviation codes are related as follows:

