5.2 Prohibited treatment

- Use of skeletal muscle anabolic agents in any form such as medications, hormones, over the counter products and nutritional supplements (other than protein) that are labeled as muscle anabolic agents.
- Anti-obesity medications, nutritional supplements, dietary interventions other than described in the protocol, or over the counter products for weight loss.
- Chronic systemic steroid treatment or systemic steroids for > 7 consecutive days for worsening of an underlying condition are not allowed during the study and within 4 weeks of screening.
- Any anti diabetic medication other than metformin or DPP4 inhibitor agent. Injectable drugs such as exenatide or pramlintide are prohibited; insulin is allowed for up to one week at a time to correct for acute hyperglycemia.
- Any product or medication known or suspected to cause weight gain, unless it is a stable anti-depressant therapy for at least 3 months before screening.

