10.3 Database management and quality control

Novartis staff or CRO working on behalf of Novartis review the data entered into the CRFs by investigational staff for completeness and accuracy and instruct the site personnel to make any required corrections or additions. Queries are sent to the investigational site using an electronic data query. Designated investigator site staff is required to respond to the query and confirm or correct the data. If the electronic query system is not used, a paper Data Query Form will be faxed to the site. Site personnel will complete and sign the faxed copy and fax it back to Novartis staff or CRO working on behalf of Novartis who will make the correction to the database. The signed copy of the Data Query Form is kept at the investigator site.

Concomitant medications entered into the database will be coded using the WHO Drug Reference List, which employs the Anatomical Therapeutic Chemical classification system. Medical history/current medical conditions and adverse events will be coded using the Medical dictionary for regulatory activities (MedDRA) terminology.

For laboratory samples processed centrally, the results will be sent electronically to Novartis (or a designated CRO).

The imaging CRO will collect all imaging data (DXA) from sites. The analysis results are then collected by the imaging CRO and then transformed into a format according to a Novartis data transfer specification. The transformed output will then be sent to Novartis data management for incorporation into the CSR. The imaging CRO will be responsible for all image data clarification forms and missing data at all sites.

At the conclusion of the study, the occurrence of any emergency code breaks will be determined after return of all code break reports and unused drug supplies to Novartis.

The occurrence of any protocol deviations will be determined. After these actions have been completed and the database has been declared to be complete and accurate, it will be locked and the treatment codes will be unblinded and made available for data analysis. Any changes to the database after that time can only be made by joint written agreement between the Biostatistics NIBR Franchise Head and the relevant NIBR TA Head.

DNA samples (optional):

Company Confidential Information

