11.1 Analysis sets

For all analysis sets, patients will be analyzed according to the study treatment(s) received.

The safety analysis set will include all patients that received any study drug.

The PK analysis set will include all patients with at least one available valid (i.e., not flagged for exclusion) PK concentration measurement, who received any study drug and with no protocol deviations that impact PK data.

The PD analysis set will include all patients with available PD data and no protocol deviations with relevant impact on PD data.

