**Table 2 Protocol deviation codes and analysis sets**

Category Deviation code	Text description of deviation	Data exclusion
	Subjects are excluded from PK analysis in case of these PDs:	Exclude subject from PK analysis set
	Subjects are excluded from PD analysis in case of these PDs:	Exclude subject from PD analysis set
	Subjects are excluded from PK and PD analysis in case of these PDs:	Exclude subject from PK and PD analysis sets

If updates to this table are needed, an amendment to the SAP needs to be implemented prior to DBL.

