## 6 Statistical methods for Pharmacodynamic (PD) parameters

All subjects within the PD analysis set will be included in the PD data analysis.

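### The visible plan runs the primary fat-mass analysis only on a set that drops whole patients for deviations and early discontinuation; an as-randomised analysis should be pre-specified beside it.

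*SAP*

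**What the plan says.** Protocol 11.1 and SAP section 4 define three sets in the visible text: safety, PK and PD.

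- **Set used.** SAP section 6 opens with "All subjects within the PD analysis set will be included in the PD data analysis". The primary objective is its subsection 6.1, which names no other set.
- **Deviations.** Protocol 11.1 states: "The PD analysis set will include all patients with available PD data and no protocol deviations with relevant impact on PD data". SAP section 4 repeats the condition ("experienced no protocol deviations with relevant impact on PD data") and adds receipt of study drug. In SAP Table 2 the action is on the whole subject: "Exclude subject from PD analysis set". Nothing visible limits this to deviations that arise before randomisation.
- **Treatment assignment.** "For all analysis sets, patients will be analyzed according to the study treatment(s) received".
- **Early discontinuation.** Protocol 11.4.1 and SAP 6.1.1 keep the end-of-treatment scan of early discontinuers out of the primary analysis. SAP 6.1.3.1 goes further and restricts the final analysis, patient by patient, to those who did not discontinue early and whose end-of-study visit falls 8 weeks, give or take 10 days, after Week 48.
- **Sensitivity.** The visible sensitivity analyses (Protocol 11.4.3 and 11.4.4; SAP 6.1.3.1 and 6.1.3.2) deal with dropout only.

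**The concern.** Randomisation protects the comparison as long as patients are not removed for what happens afterwards. Some later deviations may be linked to outcome even when everyone at the site is blinded. As an illustration, Protocol 5.2 prohibits "Anti-obesity medications, nutritional supplements, dietary interventions other than described in the protocol, or over the counter products for weight loss"; a patient who is not losing fat may be more likely to start one. The Table 2 codes are not visible, so whether this would exclude the patient is unknown.

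Removing the whole patient also loses good data. The assessment schedule has two post-baseline DXA scans before Week 48, at Days 56 and 168. The model in SAP 6.1.3 is longitudinal with categorical time and unstructured covariance, and SAP 6.1.3.1 says that it is valid under missing at random. Such a model is built to use the scans of patients who leave early, yet the same subsection removes those patients.

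At stake is the go/no-go decision that the study is meant to support (Protocol 1.4). The as-treated rule is a minor part: it differs from as-randomised only if a patient is given the wrong product.

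**Working it through.** **Inputs from Protocol 11.4.2 and 11.7.** True placebo-adjusted fat loss 6%, SD 6.5%, 24 completers per arm (34 recruited per arm, dropout at most 30%). A pass needs one-sided p below 0.10 and an estimate of at least 5%.

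**The plan's own figure.**
- SE = 6.5 × √(2/24) = 1.876.
- Significance needs 1.2816 × 1.876 = 2.40 points, so the 5% threshold decides.
- Pass probability = Φ((6 − 5)/1.876) = 70.3%. The protocol says about 70%, so it reproduces. The margin above the threshold is 1 point.

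**Two placebo patients removed.** The number removed and the correlation between exclusion and fat loss are assumptions; the documents give neither. Dropping the two poorest of 24 shifts that arm's mean by 1.02 points (simulated). With correlation ρ the shift is about 1.02ρ, and it works against the drug. SE becomes 6.5 × √(1/22 + 1/24) = 1.919.

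| ρ | Shift (points) | Pass probability |
|---|---|---|
| 0 | 0 | Φ(1/1.919) = 70% |
| 0.3 | 0.31 | Φ(0.69/1.919) = 64% |
| 0.5 | 0.51 | Φ(0.49/1.919) = 60% |
| 1 (extreme bound) | 1.02 | Φ(−0.02/1.919) = 50% |

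Simulation of the full dual rule, with a two-sample t-test standing in for the mixed model, gives the same percentages.

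**34 per arm.** The extreme shift is 0.77, so ρ = 0.3 and 0.5 give 0.23 and 0.39 points. SE with two removed is 6.5 × √(1/32 + 1/34) = 1.601. The pass probability goes from 74% to Φ(0.77/1.601) = 68% and Φ(0.615/1.601) = 65%, a smaller loss.

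**Other cases, 24 per arm, simulated.**
- Balanced, two or four removed per arm, true 6%: 69–70% at any ρ.
- Two removed from active, true 4%: 30% rises to 36% (ρ = 0.3) or 40% (ρ = 0.5).
- Two removed from active, no true effect: the false pass rate goes from 0.4% to 0.7% or 1.0%, and to 1.7% at the extreme bound.

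**Keeping deviators instead.** Suppose two placebo patients take a prohibited product that adds x points of fat loss (x is assumed). The estimate falls by 2x/24.
- x = 4: 0.33 points; Φ(0.67/1.876) = 64%.
- x = 6: 0.50 points; Φ(0.50/1.876) = 61% (60.5% before rounding).

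This is as large as the loss from excluding them, and in the same direction.

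**The case against.** The harm is assumed, not shown. The documents give no exclusion count, no imbalance and no link to outcome, and no Table 2 code can be read. In the prohibited-product example, retention can cost as much as exclusion. Such a patient may also be taken off study drug (Protocol 7.2), and would then leave the analysis through the discontinuation rule rather than the PD set. Controls exist: Protocol 10.3 says "The occurrence of any protocol deviations will be determined" before lock and code release, and SAP Table 2 adds "If updates to this table are needed, an amendment to the SAP needs to be implemented prior to DBL". Sites are blinded, DXA is read centrally, and results are withheld from investigators and patients (Protocol 6.6, 8.5, 8.5.2.1). The study is non-confirmatory (Protocol 3.1).

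Most of this stands, and it rules out four stronger readings that a reader might infer:

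- *That the plan has no as-randomised analysis at all.* SAP 6.1.3.3 and part of 6.1.3 are redacted; a supportive run may be there.
- *That the grounds for exclusion are undefined, or chosen with knowledge of treatment.* The codes are merely not visible. Protocol 6.6 and Table 6-2 do let sponsor staff see individual unblinded data at an interim, so a pre-lock decision is not necessarily a blinded one. Whether any interim overlaps with exclusion decisions is unknown.
- *That the rule inflates false success.* Under no effect the pass rate stays below 2% even in the extreme two-patient case, and outcome-linked placebo exclusions work against the drug.
- *That the PD set must be replaced as the primary set.* Both choices can bias the estimate, so this is an estimand choice.

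What the objection does not remove: the visible sensitivity analyses do not test deviation exclusions, and the patient-level rule in SAP 6.1.3.1 sits badly with a missing-at-random model.

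**Conclusion.** The concern holds as a gap in the visible plan. The primary analysis rests on a set that is in effect per-protocol and as treated, narrowed further by SAP 6.1.3.1, with no visible as-randomised result to set against it. Its size is conditional. With two one-arm, outcome-linked exclusions the estimate moves about 0.3 to 0.5 points of a 1-point margin, which costs 6 to 10 percentage points of pass probability at 24 per arm and less at 34. Balanced or outcome-unrelated exclusions barely matter. The risk is to the decision near the 5% threshold, in either direction. Severity is low to moderate. A pre-specified second analysis is worth adding; the documents do not show that the current primary result would be wrong.

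**What to change.** 1. Pre-specify a full analysis set: all randomised, treated patients with a baseline DXA, analysed as randomised with every on-schedule DXA scan. Run the same fat-mass model on it and report the dual-criterion result for this set and the PD set. The sponsor states in advance which one leads.
2. State that the patient-level exclusion in SAP 6.1.3.1 does not apply to this set. Early discontinuers contribute their scheduled Day 56 and Day 168 scans where taken; their early end-of-treatment scan is still not counted as Week 48 (Protocol 11.4.1, SAP 6.1.1). Their Week 48 outcome then rests on missing at random, which the planned dropout sensitivity analyses address.
3. Finalise Table 2 before any unblinded interim, and have later deviations classified by staff without treatment codes.

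If the redacted SAP 6.1.3.3 already holds such a run, only items 2 and 3 and the side-by-side reporting remain.

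Cost: one set definition, one more model run, and a sentence each for items 2 and 3. Downside: retained deviators can bias the estimate by as much as excluding them would, which is the reason to show both results.
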